MRIs will be performed at Week 13 (Cycle 4, Day 1 visit of Part 1 [P1-C4D1]) and Week 25. If disease progression is indicated clinically or by local radiologic assessment according to RECIST 1.1 at or after Week 13 but before Week 25, the Investigator may request a central review for evaluation of disease progression. Any disease progression before Week 25 must be verified by a central MRI reading. If a central reading confirms RECIST 1.1-defined disease progression, treatment assignment will be unblinded, and subjects receiving placebo will be eligible for early entry into Part 2 of the study. Effective 30 Sep 2016, subjects receiving placebo will be discontinued instead of being eligible to enter Part 2. Subjects receiving pexidartinib will be discontinued from the study unless the Investigator and the Sponsor's Medical Monitor judge that the subject would potentially benefit from continued treatment with pexidartinib. For those subjects who undergo surgical resection after Week 25, an MRI will be performed 4 months after surgery.

Part 2 will continue until all subjects have either reached at least the Week 49 visit, ie, an additional 24 weeks of study treatment beyond the placebo-controlled phase, or withdrawn from the trial (Figure 3.1). As in Part 1, dose reductions, interruptions, and re-escalations after previous reductions for toxicity are permitted according to pre-specified guidelines. Subjects who complete Part 2 will be eligible to continue pexidartinib treatment for study of longer efficacy and safety follow-up assessed per the schedule in Part 2 or to enter a separate protocol to continue receiving pexidartinib.

Figure 3.1: Study Schematic*

* Effective 30 Sep 2016, subjects on placebo are no longer allowed into Part 2 to receive open-label pexidartinib.

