4.2. Removal of Subject From Therapy

If a subject is withdrawn from the study, the Investigator will complete and report the observations as thoroughly as possible up to the date of withdrawal including the date of last treatment and the reason for withdrawal.

If the subject is withdrawn due to an AE, the Investigator will follow the subject until the AE has resolved or stabilized.

Subjects can only be considered for surgical resection after the completion of Part 1.

If a subject undergoes surgical resection of the tumor after Part 1, the study treatment is recommended to be discontinued 1-3 weeks before the surgery. The subject will be followed for surgery and its outcome and not considered as discontinued from the study. Data collection for the surgery and its outcome may continue in a separate protocol. If a subject undergoes surgical resection prior to completion of Part 1, the information about surgery and its outcome will still be collected.

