For the P2-C1D1 visit (Week 25), subjects should be told to NOT take the morning dose of study treatment before their visit and to bring all unused capsules to the clinic for accountability. Subjects who will continue into Part 2 will be given open-label pexidartinib for the first time at

that visit, taking the same number of capsules per day as they were taking at the end of Part 1, ie, a maximum dose of 800 mg/d pexidartinib.

Between clinic visits, subjects will administer their study treatment at home and record the dosing information in the study dosing diary. Missed doses (those generally outside of a \pm 2-hour dosing window) should be skipped and NOT administered as a double dose at the next dosing time point. Subjects who vomit their dose should be instructed NOT to make up that dose.

Further details on study treatment administration are contained in the separate Pharmacy Manual.

For subjects who undergo surgical resection of their tumor, study treatment will be discontinued before surgery and will not be restarted after surgery.

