7.4. General Statistical Considerations

Continuous variables will be summarized by the number of observations, mean, standard deviation, median, 25th and 75th percentile, and minimum and maximum values. Categorical variables will be summarized using frequency counts and percentages.

In general, the baseline value for an efficacy variable, including that for a PRO variable, is the last non-missing value before randomization. The baseline value for a safety variable is the last non-missing value before the first dose of study treatment. The exceptions are several special variables in Part 2, such as the tumor response and duration of response variables evaluated for pexidartinib treatment for subjects randomized to placebo in Part 1; in such cases, the baseline for Part 2 is defined as the last non-missing value before the first dose in Part 2. Further details are contained in the following sections and in the Statistical Analysis Plan (SAP).

For the primary efficacy endpoint and secondary efficacy endpoints with the exception of duration of response, treatment comparison at Week 25 will be performed based on the data collected during the visits between baseline and Week 25. Point estimate and accompanying 95% confidence interval (CI) will be computed. For duration of response, Kaplan-Meier product limit methodology will be utilized to provide estimates, including those for the median and 25th and 75th percentiles.

All statistical tests will be 2-sided. Unless otherwise specified, all tests will be carried out at the alpha = 0.05 level of significance.

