7.6.3. Additional Efficacy Analyses

Additional efficacy endpoints to be analyzed at Week 25, with the exception of duration endpoints or otherwise indicated, include:

- Proportion of responders on the BPI Worst Pain NRS item and analgesic use by BPI-2p definition (see below)
- Proportion of responders on the BPI Worst Pain NRS item and analgesic use by BPI-50 (see below)
- Proportion of responders on the Worst Stiffness NRS item
- Proportion of responders on the PROMIS Physical Function Scale
- Mean change from baseline in the BPI Worst Pain NRS item
- Patient Global Impression of Change item for tumor-related stiffness and Patient Global Rating of Concept item for ability to carry out every day physical activities.
- Duration of BPI-based symptom response, analyzed for BPI-30, BPI-50 and BPI-2p.
- Results of the Surgical Assessment Questionnaire in Part 1.
- Response based on the change in the SSD of the tumor on MRI, referred to as “modified RECIST 1.1–SSD”

- Amount of joint/tissue damage (eg, bone erosion, bone edema, cartilage loss) assessed on MRI based on adaptations of the RAMRIS and WORMS
- Analgesic use expressed as morphine-equivalent doses in Part 1²²
- EQ-5D-5L parameters in Part 1
- Major HCRU and productivity in Part 1
- Duration of response based on MRI and modified RECIST 1.1-SSD
- Response based on the most disturbing symptom of pain, stiffness, or compromised ability to carry out everyday activities.
- Proportion of subjects receiving surgical resection of their tumor by 25 weeks, 49 weeks, 73 weeks, and 97 weeks of pexidartinib treatment

For responder analysis based on the BPI Worst Pain NRS item and analgesic use, a BPI-2p responder will be defined as a subject who (i) experienced a decrease of at least 2 points in the mean BPI Worst Pain NRS item and (ii) did not experience a 30% or greater increase in narcotic analgesic use, comparing data collected during a 7-day period prior to the current visit for responder assessment with baseline values collected prior to the first dose of study treatment. A BPI-50 will have the same definition except the subject must experience a decrease of at least 50% in the mean BPI Worst Pain NRS item. Subjects who do not provide data for the endpoint will be considered to be non-responders. Definition for increase in analgesic use is outlined in Section 6.4.11. See SAP for further details.

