The endpoints involving the PRO assessments, amount of joint/tissue damage, response based on MRI and modified RECIST 1.1-SSD, and duration of response will be analyzed using the same methods as those used for the primary and secondary endpoints.

Duration of BPI symptom response for a responder is the interval from the first time BPI symptom response is documented to the first subsequent time point when the BPI symptom response is not met. The definition applies to BPI symptom response of BPI-30, BPI-50 and BPI-2p. Duration of BPI symptom response will be summarized in a way similar to that for duration of tumor response by RECIST 1.1.

For subjects who undergo surgical resection, the surgery-related data will be listed, including those collected in the separate protocol, if applicable. Proportion of subjects receiving surgical resection of their tumor by 25 weeks of pexidartinib treatment will be calculated regardless of whether blinded or open-label pexidartinib treatment, or both, was taken. The numerator is the number of subjects having the surgical resection of the tumor within 36 weeks of the first treatment of pexidartinib, taking into account the 12 weeks allowable window. The denominator is the number of subjects who complete at least 24 weeks of pexidartinib treatment. Likewise, the proportion of subjects receiving surgical resection of their tumor by 49 weeks, 73 weeks, and 97 weeks of pexidartinib treatment will be calculated similarly.

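### The surgical resection ratio counts operated subjects who cannot be in its denominator, so on its natural extension to 49, 73 and 97 weeks it is not a proportion and overstates resection

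*Combined protocol and SAP*

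**What the plan says.** Section 7.6.3 (Additional Efficacy Analyses) lists this endpoint: "Proportion of subjects receiving surgical resection of their tumor by 25 weeks, 49 weeks, 73 weeks, and 97 weeks of pexidartinib treatment". It writes out the 25-week version only. For the top of the ratio: "The numerator is the number of subjects having the surgical resection of the tumor within 36 weeks of the first treatment of pexidartinib", which is 24 weeks of treatment plus a 12-week surgical window. For the bottom: "The denominator is the number of subjects who complete at least 24 weeks of pexidartinib treatment". Blinded and open-label drug both count. The other three landmarks get one clause: "by 49 weeks, 73 weeks, and 97 weeks of pexidartinib treatment will be calculated similarly". No window, denominator or rule for incomplete follow-up is given for them.

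Four other provisions bear on it:

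- Section 5.2, for subjects who have a resection: "study treatment will be discontinued before surgery and will not be restarted after surgery".
- Section 4.2: "Subjects can only be considered for surgical resection after the completion of Part 1". The same section nevertheless provides for collecting data on surgery that happens before Part 1 is complete.
- Section 3.1: Part 2 runs until every subject has reached Week 49 or withdrawn, and "Subjects who complete Part 2 will be eligible to continue pexidartinib treatment for study of longer efficacy and safety follow-up". Subjects may instead move to a separate protocol or, under Section 4.2.1, to commercial drug.
- Section 7.4: "Further details are contained in the following sections and in the Statistical Analysis Plan (SAP"). No separate SAP text was available for this review.

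**The concern.** The endpoint should show how often the tumour is resected as time on pexidartinib lengthens. Dividing by treatment completers works against that, because surgery itself ends treatment. The ordinary surgical patient, who finishes Part 1, stops drug at about Week 30 and is operated on soon after, falls inside all three later windows but completes neither 48, 72 nor 96 weeks. Operations accumulate in the numerator while the denominator loses the operated subjects and everyone else who stops. The result can mislead in either direction, depending on how a programmer interprets the one-clause extension. A reader of the study report would see a figure labelled as a proportion that is not one.

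**Working it through.** **Windows.** The written one reproduces: 24 + 12 = 36 weeks. Carried forward (inferred): 48 + 12 = 60, 72 + 12 = 84, 96 + 12 = 108.

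**Structural check, no rates needed.** Suppose 50 subjects complete 24 weeks, 10 of them stop and are operated on near Week 30, and the other 40 complete 48 weeks. The natural extension gives 10/40 = 25% at 49 weeks, and none of the 10 is among the 40. The share of 24-week completers operated on is 10/50 = 20%. Limiting the numerator to 48-week completers gives 0/40 = 0%.

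**Size under assumed rates.** The documents give no surgery or stopping rates. Assume 63 subjects start pexidartinib (the planned arm size, Section 7.12), other stopping is d = 0.006 per week from Week 1, stopping for surgery is s = 0.001 per week after Week 24, and surgery is 2 weeks after last dose (Section 3.1 recommends 1–3). Let h = s + d = 0.007. For landmark T = 24, 48, 72 or 96:

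- 24-week completers: 63·exp(−0.006·24) = 54.55
- share of these still on drug at T: S = exp(−h(T − 24))
- share operated on by T + 12: C = (s/h)·[1 − exp(−h(T + 12 − 2 − 24))]
- share operated on who stopped before T: E = (s/h)·(1 − S)
- natural extension = C/S; fixed 24-week denominator = C; numerator limited to landmark completers = (C − E)/S; share of numerator outside the denominator = E/C

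At 97 weeks (T = 96): S = exp(−0.504) = 0.604; C = (1/7)(1 − exp(−0.574)) = 0.0624; E = (1/7)(1 − 0.604) = 0.0566.

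| Landmark | Natural extension | Fixed 24-week completers | Landmark completers only | Outside denominator |
|---|---|---|---|---|
| 25 wk | 1.0% | 1.0% | 1.0% | 0% (by construction) |
| 49 wk | 3.6% | 3.0% | 1.0% | 73% |
| 73 wk | 6.7% | 4.8% | 1.0% | 86% |
| 97 wk | 10.3% | 6.2% | 1.0% | 91% |

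The closed form is a ratio of expected counts, 3.40/32.95 = 10.3% at 97 weeks. Averaging the ratio over 40,000 simulated trials of 63 gives 10.6%, because the denominator varies; the simulated 49- and 73-week values are 3.6% and 6.8%.

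**Sensitivity.** With surgery at 0.05% or 0.2% per week, the simulated 97-week natural extension is 5.2% or 22.0%, against 3.2% or 12.0% of 24-week completers. In a second model with 85% completing 24 weeks, and per further 24 weeks 15% stopping for surgery and 25% for other reasons, the 97-week ratio is 15.2/13.9 = 109%.

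**The 25-week rule.** The 0% above holds only because the model has no placebo crossovers and no surgery in Part 1. Placebo subjects could enter Part 2 before 30 September 2016, and could be operated on after less than 24 weeks of pexidartinib. Add 30 crossovers (assumed) at the same rates from their first dose. Operated on within 36 weeks: 30·(1/7)(1 − exp(−0.007·34)) = 0.91, of whom 30·(1/7)(1 − exp(−0.007·24)) = 0.66 stopped before 24 weeks. The other 63 contribute 54.55·0.00966 = 0.53. Outside the denominator: 0.66/(0.91 + 0.53) = 46%.

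**The case against.** The strongest reply is that this is a descriptive endpoint, that Section 7.6.3 lists the surgical data subject by subject anyway, and that a separate SAP may define the later landmarks. All of that is true and keeps the point minor. With rare surgery the difference is also small: at 0.05% per week the 49-week figures are 1.8% and 1.5%, with an average numerator of 0.8 subjects. But none of this removes the mismatch, which follows from Sections 7.6.3 and 5.2 alone and is present in the rule that is written out.

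Four further inferences are tempting and should not be drawn:

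- **That every alternative ratio is biased.** Restricting the numerator to landmark completers does drop all earlier operations, so the figure stays flat. The written numerator carries no such restriction, so this interpretation is also strained. A fixed 24-week-completer denominator is different: with complete follow-up it is exactly the share of those completers operated on. It is low only where follow-up or capture of surgery is incomplete. In the second model, at 10% surgery and 20% other stopping per 24 weeks, with follow-up assumed to end between Weeks 49 and 110, it gives 11.6/15.2/16.2% at 49/73/97 weeks against 11.9/17.6/21.6% with full follow-up. The shortfall is slight at 49 weeks.
- **That the 25-week figure is sound.** The bar on surgery during Part 1 does not protect it, as shown above for crossovers. Section 4.2 itself foresees resection before Part 1 is complete.
- **That later denominators shrink only through stopping drug.** Subjects can also leave while on drug, to a separate protocol or commercial supply.
- **That surgery in subjects with progression is captured for only 28 days.** Their last scheduled evaluation is then, but Section 15.4 and the surgical-data footnotes to Tables 15.2 and 15.3 cover surgery within 12 weeks of last dose, with no exception for progression.

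**Conclusion.** The point holds, as a minor one. At every landmark the ratio admits subjects to the numerator whom the denominator excludes. On the natural extension this overstates resection, increasingly with time: 10.6% at 97 weeks against 6.2% of 24-week completers operated on, with about 91% of the numerator outside the denominator. Those sizes rest on assumed constant rates and inferred windows; the mismatch itself rests on neither. How often it affects the 25-week figure depends on the number of crossovers and early operations, which the documents do not give. A reader might infer that the trial's efficacy conclusions are touched. They are not: the endpoint is outside the testing hierarchy, and the primary analysis, alpha and sample size stand.

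**What to change.** At all four landmarks, replace the ratio with wording such as: *Cumulative incidence of surgical resection will be estimated from first pexidartinib dose, blinded or open-label, in all subjects who received pexidartinib, with 95% CI and number at risk at 36, 60, 84 and 108 weeks. Subjects without resection are censored 12 weeks after last dose, or at last contact if earlier; follow-up continues in a separate protocol only if surgical data are collected there. Numbers censored will be given by reason.* Add a sensitivity analysis that treats stopping without surgery as a competing event.

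The choice between these two estimators matters. Under the main assumptions, subjects at risk late in follow-up have an operation rate of 0.001·exp(0.014)/[1 + (1/7)(exp(0.014) − 1) + (6/7)(exp(0.084) − 1)] = 0.00094 per week. Over the 82 weeks from Week 26 to Week 108 this gives 1 − exp(−0.077) = 7.4% with censoring. As a competing event it is 3.40/63 = 5.4%.

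The cost is a text change and a standard time-to-event program on data already planned for collection, with no added visits. There are two downsides. The quantity moves from weeks of treatment in completers to time since first dose in all treated subjects. Censoring may also be informative, since those who stop may differ in later surgery, and operations more than 12 weeks after last dose are not systematically captured. If the sponsor keeps a ratio, each landmark's numerator and denominator should be written out, with its direction of bias.

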7.6.4. Subgroup Analyses

The primary endpoint and BPI Worst Pain NRS item will be also analyzed in the following subgroups of the ITT population:

- Subjects with disease located in large joints (shoulder, elbow, hip, or knee);
- Subjects with disease located in small joints (joints other than the shoulder, elbow, hip, or knee);
- Subjects with disease located in the knee;
- Subjects with GCT-TS type of TGCT;
- Subjects with PVNS type of TGCT;
- Subjects with lower extremity tumors;
- Subjects with upper extremity tumors;
- Subjects at US sites;
- Subjects at sites outside of the US;
- Subjects at sites in the EU region only.

In each subgroup defined above, the analysis will be carried out using the same type of methodology as described for the overall analysis of the corresponding endpoint. These results will be considered exploratory because of the multiplicity issue and also smaller sample sizes that cannot be pre-specified. For subgroups without an adequate number of subjects, the analysis will not be performed.

7.7. Pharmacodynamics/Biomarkers

Blood samples collected at specified time points will be analyzed for markers of pexidartinib exposure and for exploratory biomarkers, including CSF-1 and adiponectin.

Available and consented archival tissue specimens from PVNS/GCT-TS tumors will be collected and stored for exploratory biomarkers related to pexidartinib and/or disease. Plasma will be analyzed for markers of pexidartinib exposure and for exploratory biomarkers, including CSF-1 and adiponectin. No formal statistical analysis of PDy endpoints will be performed.

Pharmacodynamic data from each assay will be listed and possible relationships between PK and PDy variables may be explored. Any biological activity will be described.

Biomarker data will be summarized using descriptive statistics by treatment and visit. Exposure-biomarker data will be analyzed graphically and may be modeled if data permit.

7.8. Pharmacogenomic Analysis

7.8.1. Genomic or Genetic Banking and Analysis

A single blood sample (10 mL) for pharmacogenomics analysis will be collected from each subject who consent to this test. Pharmacogenomic sample may also be collected from discontinued subjects who provide consent. Participation in this part of the study is optional for all subjects.

The following procedures will be used for the long-term preservation (banking) of DNA specimens extracted from subjects' blood samples. Pharmacogenomic samples may be analyzed for genes involved in absorption, distribution, metabolism, elimination, safety, and efficacy of pexidartinib. Additionally, samples may be analyzed for genes involved in pexidartinib related signaling pathways, or to examine diseases or physiologic processes related to pexidartinib. DNA samples will not be immortalized or sold to anyone. This information may be useful in increasing the knowledge of differences among individuals in the way they respond to the study drug, as well as helping in the development of new drugs or improvement of existing drugs.

Specimen shipping and handling details will be included in the laboratory manual.

7.8.1.1. Disclosure of the Results of Genomic or Genetic Analysis

Because the nature and value of future pharmacogenomic research cannot be known at this time, any results obtained from research involving pharmacogenomic samples will not be disclosed to the subject or Investigators now or in the future.

7.8.1.2. Storage and Disposal of Specimens for Genomic or Genetic Banking and Analysis

Samples will be retained until exhausted or until the Sponsor requests disposition.

If the subject withdraws consent, the banked blood samples will be properly and promptly disposed of. However, the data will not be discarded if genetic analysis has been completed before the subject withdraws consent.

7.9. Pharmacokinetics and Exposure–Response Analyses

Plasma–concentration time data for pexidartinib will be summarized by visit and time using descriptive statistics. Plasma–concentration data from these samples will be analyzed using a PopPK approach using nonlinear mixed effects modeling. Data from Phase 1 studies will be used to inform and stabilize the structural PK model and will be pooled with Phase 3 data to assess and characterize the inter- and intra-subject variability in PK and to identify significant covariates. PK parameters will include apparent clearance and volume of distribution along with transfer rate constants such as absorption and elimination rates. Additionally, based on post hoc Bayesian methods, estimates of exposure such as C_{max} , C_{trough} , C_{av} and AUC_{ss} may also be reported.

Exposure–Response

Bayesian individual exposures of pexidartinib from the PopPK analysis will be used to explore relationships between exposure metrics and biomarkers and safety and efficacy endpoints. These analyses will be summarized in a separate report.

